#### **4. STUDY POPULATION**

##### **4.1 Population (base)**

During the time that the study is open, we will select consecutive patients based on the information provided by the referring physician on the requisition for the study.

##### **4.2 Inclusion criteria**

In order to be eligible to participate in this study, a subject must meet all of the following criteria:

- referred to Isala for a clinically indicated FDG-PET/CT scan
- suspected or proven lung cancer, esophageal cancer or breast cancer, either as a primary diagnosis or follow-up study
- signed informed consent

##### **4.3 Exclusion criteria**

A potential subject who meets any of the following criteria will be excluded from participation in this study:

- age < 18 years
- incapacitated adults
- prisoners
- pregnant patients
- unable to undergo two consecutive PET/CT scans

#### 4.4 Sample size calculation

From the detailed research questions stated in chapter 2, a rough estimate of the number of required subjects will be calculated, although this is difficult because the clinical performance parameters for digital PET are not available yet. The only qualitative impression from preliminary images is that image quality and detection properties are going to be significantly better.

Sample size calculations are performed for primary objectives 1.1 and 1.3. We do not formally calculate estimates for the remaining objectives, but estimate that there will be ample scans to answer these objectives, once the first questions have been answered. Furthermore in general, we expect that around 10% of the patients that are included in this study show a negative PET/CT scan, without the presence of malignant disease. Therefore, we will increase the required number of patients with 10%, to reach the required number of patients with malignancies for this study.

The sample size calculation is performed for the three subgroups of cancer types separately. However, the sample size calculation for patients with lung cancer and patients with breast cancer is identical, due to a roughly comparable disease incidence (and thus a comparable amount of FDG-PET/CT scans acquired) and a comparable expected performance. For esophageal cancer, a separate sample size calculation is provided, due to a lower disease incidence.

##### Sample size calculation for patients with lung cancer and patients with breast cancer:

###### **Objective 1.1 What is the difference in the number of lymph node metastases?**

*For power-calculations we translated this question into: does digital PET detect more, fewer or identical numbers of lymph node metastasis? We would like to be able to detect a 20% difference, if present. This level is generally considered relevant in obtaining a new type of scanner. Using the two-tailed sign-test, assuming a power of 80% and a p value of 0.05, this requires the inclusion of 49 subjects. After applying the 10%-correction for the inclusion of negative PET/CT scans, the number of required subjects is 54.*

###### **Objective 1.3 What is the difference in the N status?**

*For power-calculations we translated this question into: is the N-status on digital PET equal, lower or higher as compared to conventional PET? We would like to be able to detect a 16% difference, if present. Using the two-tailed sign-test, assuming a power of 80% and a p value of 0.05, this requires the inclusion of 79 subjects. After applying the correction for negative PET/CT scans, the number of required subjects is 87.*

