**Objective 1.1 What is the difference in the number of lymph node metastases?**

*For power-calculations we translated this question into: does digital PET detect more, fewer or identical numbers of lymph node metastasis? We would like to be able to detect a 20% difference, if present. This level is generally considered relevant in obtaining a new type of scanner. Using the two-tailed sign-test, assuming a power of 65% and a p value of 0.10, this requires the inclusion of 28 subjects. After applying the correction for negative PET/CT scans, the number of required subjects is 31.*

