**Objective 1.3 What is the difference in the N status?**

*For power-calculations we translated this question into: is the N-status on digital PET equal, lower or higher as compared to conventional PET? We would like to be able to detect a 16% difference, if present. Using the two-tailed sign-test, assuming a power of 65% and a p value of 0.10, this requires the inclusion of 42 subjects. After applying the correction for negative PET/CT scans, the number of required subjects is 46.*

From all above calculations, we aim to include 90 patients with lung cancer, 90 patients with breast cancer and 45 esophageal cancer patients, for a total of 225 patients.

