#### 7.1.1 Primary objective: diagnostic outcome of the PET/CT studies

For each patient separately, the diagnostic outcome for the conventional and digital PET/CT study will be compared. Measured ordinal differences in for example the N-status or the TNM classification will be assessed based on two methods. The first method is based on the sign test, in which the comparison results in an agreement or a disagreement. The second method is based on the Wilcoxon signed-ranked test, in which the amount of disagreement is also taken into account. Moreover, we will calculate agreement percentages on the diagnostic outcome between both systems. Furthermore, using validation results as a reference, we will determine the sensitivity, specificity and accuracy for both NM physicians based on the following formulas:

$$\text{Sensitivity} = N_{PET \text{ positive}} / N_{\text{true positive}}$$

$$\text{Specificity} = N_{PET \text{ negative}} / N_{\text{true negative}}$$

$$\text{Accuracy} = (N_{PET \text{ positive}} + N_{PET \text{ negative}}) / (N_{\text{true positive}} + N_{\text{true negative}})$$

To test whether differences in sensitivity, specificity and accuracy between conventional and digital PET/CT are significant, we will apply the McNemar paired proportion test. A p value of less than 0.05 will be considered to indicate statistical significance.

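### The N-status sample size (79, which sets 90 per group) counts patients whose two scans differ but is used as all patients with malignancy, so the stated 80% power rests on an unstated share of ties and an unstated split

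*Combined protocol and SAP*

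**What the plan says.** Section 4.4 sizes the study on objectives 1.1 and 1.3 only, separately by tumour type.

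- **Objective 1.3, lung and breast.** The question is put as "is the N-status on digital PET equal, lower or higher as compared to conventional PET", with a 16% difference to be detected. "Using the two-tailed sign-test, assuming a power of 80% and a p value of 0.05, this requires the inclusion of 79 subjects". This becomes 87 after the correction for negative scans and is rounded to 90 per group.
- **Objective 1.1, lung and breast.** The question is "does digital PET detect more, fewer or identical numbers of lymph node metastasis", with a 20% difference. The size is 49, or 54 after correction.
- **Esophageal cancer.** For the 20% difference in objective 1.1: "assuming a power of 65% and a p value of 0.10, this requires the inclusion of 28 subjects". For the 16% difference in objective 1.3: "assuming a power of 65% and a p value of 0.10, this requires the inclusion of 42 subjects". The target is 45.
- **Inflation.** The only allowance is for patients without malignant disease: "Therefore, we will increase the required number of patients with 10%, to reach the required number of patients with malignancies for this study".

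Section 7.1.1 gives the matching analysis: "The first method is based on the sign test, in which the comparison results in an agreement or a disagreement". A Wilcoxon signed-rank test is the second method. It adds: "Moreover, we will calculate agreement percentages on the diagnostic outcome between both systems".

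Neither section gives the expected share of patients with equal results, the split between higher and lower among the rest, or what the 16% and 20% are percentages of.

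**The concern.** A sign test drops every patient whose two results are the same. A sample size from a sign test calculated without ties is therefore a number of differing patients. The plan expects ties: both objectives name an equal or identical result, and 7.1.1 plans to report agreement. Yet the 10% correction covers only patients with no malignancy. A patient with malignancy who is N0 on both scans, or N2 on both, is also a tie, and nothing is added for that.

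Objective 1.3 matters most because it sets the 90 per group. Objective 1.1 in lung and breast needs only 49 differing patients, so it has slack.

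Section 4.4 is the only basis given for 90/90/45. If the split is near 66:34 and many patients have equal N status, power for objective 1.3 is well below 80%, and a non-significant result would be weak evidence that the scanners stage alike.

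**Working it through.** **Inputs from section 4.4.** Two-sided sign test; differences of 20% and 16%; alpha 0.05 with 80% power (lung, breast); alpha 0.10 with 65% power (esophageal); 10% negative scans; targets 90, 90 and 45.

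**Assumptions.** The documents give neither the share q of diseased patients whose scans differ nor the split p among them. Both are varied below.

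**Step 1: reproduce the plan's sizes.** Exact two-sided sign test of 0.5 against p = 0.5 + difference, every patient untied, smallest n that reaches the target power:

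| Group, objective | Split | Alpha | Target | Smallest n | Power at n | Power at n - 1 |
|---|---|---|---|---|---|---|
| Lung/breast, 1.1 | 70:30 | 0.05 | 80% | 49 | 81.0% | 74.9% |
| Lung/breast, 1.3 | 66:34 | 0.05 | 80% | 79 | 80.7% | 76.4% |
| Esophageal, 1.1 | 70:30 | 0.10 | 65% | 28 | 68.3% | 57.7% |
| Esophageal, 1.3 | 66:34 | 0.10 | 65% | 42 | 66.0% | 58.0% |

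All four match the plan exactly. The arithmetic is right; the question is which patients it counts.

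**Step 2: diseased patients available.** 90 x 0.9 = 81 in lung and in breast; 45 x 0.9 = 40.5, taken as 40, in esophageal.

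**Step 3: power with ties.** Power = sum over m of P(M = m) x (exact sign-test power with m differing patients), where M is Binomial(N, q). With N = 81 and alpha 0.05:

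| Share differing, q | Objective 1.3 at 66:34 | Objective 1.1 at 70:30 |
|---|---|---|
| 100% | 82% | 96% |
| 80% | 71% | 89% |
| 60% | 57% | 78% |
| 50% | 48% | 69% |
| 40% | 38% | 57% |
| 20% | 18% | 28% |

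**Step 4: smallest share that gives 80% with 81 patients** (searched in steps of one point): 99% at 66:34, 64% at 70:30, 42% at 75:25, 29% at 80:20, 16% at 90:10.

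**Step 5: the other natural reading.** If 16% is a net difference (higher minus lower) over all diseased patients, then p = (1 + 0.16/q)/2. With N = 81:

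| q | Split | Power |
|---|---|---|
| 20% | 90:10 | 92% |
| 25% | 82:18 | 81% |
| 30% | 77:23 | 71% |
| 40% | 70:30 | 57% |
| 50% | 66:34 | 48% |
| 100% | 58:42 | 29% |

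A 20% net difference gives 97% at q = 25% and 79% at q = 40%. No single q makes this reading reproduce all four sizes: at q = 25%, 49 and 79 patients give 80%, but 28 and 42 give 57% against the stated 65%.

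**Step 6: esophageal group, objective 1.3 at 66:34.** With 40 diseased patients and alpha 0.10, power is 62% with no ties and 28% if 40% differ. At alpha 0.05 with no ties it is 49% (54% with 42 patients).

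**The case against.** - **The plan never says that 79 counts differing patients.** True; this is inferred. But four exact matches from one method leave little doubt about the calculation, and a size from a sign test without ties is by construction a count of differing patients.
- **A benign reading exists.** If 0.66 means the proportion higher plus half the proportion equal, ties do no harm: with 81 patients, power is 82% with no ties, 89% if 80% differ and 97% if 60% differ. That is a net difference of 32 points, twice the stated 16%, and it is not written in the plan either. It adds to the ambiguity.
- **The size is presented as rough, because performance data for digital PET did not exist, and digital PET was expected to detect more.** This is fair. The sponsor cannot be asked for a known tie share, and one-sided disagreement would help power. It argues for a range, not for an unqualified 80%.
- **The Wilcoxon test is also planned.** It gains little from zero differences, so it does not remove the problem.
- **Some figures look more precise than they are.** This stands. Exact power moves in small jumps: at 66:34 it is 79.4% with 98% differing, so the 99% is best read as nearly all patients. The esophageal 62% becomes 58% with 41 patients in place of 40.
- **The 0.10 level is stated only for sizing, and the 0.05 in 7.1.1 follows the McNemar test.** Also true, so this is a point to reconcile, not a plain contradiction.

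**Conclusion.** The concern holds. The number 79 is correctly computed, but for patients whose N status differs at a 66:34 split; section 4.4 applies it to all patients with malignancy. The stated 80% is reached at 66:34 only if nearly all of the 81 diseased patients differ. It is reached with about 64%, 42%, 29% or 16% differing at 70:30, 75:25, 80:20 or 90:10. If 16% is meant as a net difference over all patients, it is reached only if about 25% or fewer differ.

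Every power figure with ties rests on an assumed share and split, and on 10% negative scans as in 4.4. The study is not shown to be underpowered. What is shown is that the flat 80% cannot be relied on as written. The same gap affects 49, 28 and 42, with slack for 49. The point should be fixed.

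**What to change.** 1. **Section 4.4, meaning.** Say whether the 20% and 16% are a shift in the split among differing patients or a net difference over all patients. State that 49, 79, 28 and 42 come from a sign test without ties at 70:30 and 66:34, and so count differing patients.
2. **Section 4.4, power.** Replace the flat 80% and 65% with power for 81, 81 and 40 diseased patients over a stated range of shares and splits. Possible wording: *With 81 diseased patients, power for N status is 80% if at least about 99% (nearly all), 64%, 42%, 29% or 16% of patients differ, at a split of 66:34, 70:30, 75:25, 80:20 or 90:10 respectively.* This table holds under any reading of the 16%.
3. **Section 7.1.1, level.** State the sign-test significance level for the esophageal group so that it agrees with 4.4, or restate that group's power at 0.05.
4. **Optional.** Add a supportive sign test pooled over tumour types, beside the per-tumour analyses and not in their place. With about 202 diseased patients (225 x 0.9 = 202.5) at 66:34, unstratified, power is about 80% if 40% differ and 48% if 20% differ.

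**Cost.** Wording in two sections, notified to the METC as an amendment, with no extra patients or procedures. The stated power becomes conditional and, at 66:34, less favourable. For scale only, 80% power at 66:34 would need 101 diseased patients per group if 80% differ, 135 if 60% and 203 if 40%.

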##### Sample size calculation for patients with esophageal cancer:

The incidence of esophageal cancer is much lower as compared to lung and breast cancer. As a consequence, the number of FDG-PET/CT scans that is acquired for this

patient group is much lower. Therefore, we accept a lower level of power (65%) and a lower significance level ( $p < 0.10$ ) for the sample size calculation for this specific tumor type.

**Objective 1.1 What is the difference in the number of lymph node metastases?**

*For power-calculations we translated this question into: does digital PET detect more, fewer or identical numbers of lymph node metastasis? We would like to be able to detect a 20% difference, if present. This level is generally considered relevant in obtaining a new type of scanner. Using the two-tailed sign-test, assuming a power of 65% and a p value of 0.10, this requires the inclusion of 28 subjects. After applying the correction for negative PET/CT scans, the number of required subjects is 31.*

**Objective 1.3 What is the difference in the N status?**

*For power-calculations we translated this question into: is the N-status on digital PET equal, lower or higher as compared to conventional PET? We would like to be able to detect a 16% difference, if present. Using the two-tailed sign-test, assuming a power of 65% and a p value of 0.10, this requires the inclusion of 42 subjects. After applying the correction for negative PET/CT scans, the number of required subjects is 46.*

From all above calculations, we aim to include 90 patients with lung cancer, 90 patients with breast cancer and 45 esophageal cancer patients, for a total of 225 patients.

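### The oesophageal target of 45 is below the plan's own requirement of 46 for N status (47 if the 10% allowance is divided out), and the power should be restated as about 61%, not 65%

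*Combined protocol and SAP*

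**What the plan says.** Section 4.4 sizes Objectives 1.1 and 1.3 separately by tumour type. It expects about 10% of included patients to have a negative scan and, to compensate, says "we will increase the required number of patients with 10" per cent.

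For oesophageal cancer, where referrals are scarcer, the standards are openly relaxed: "we accept a lower level of power (65%) and a lower significance level". For Objective 1.3 the effect is given as "We would like to be able to detect a 16% difference, if present", and the base figure as "Using the two-tailed sign-test, assuming a power of 65% and a p value of 0.10, this requires the inclusion of 42 subjects". The inflated figure follows: "After applying the correction for negative PET/CT scans, the number of required subjects is 46". The closing sentence of section 4.4 presents the targets as the result of these calculations and gives "45 esophageal cancer patients, for a total of 225 patients", with 90 each for lung and breast. No reason is given for setting 45 below 46.

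**The concern.** There are two slips. First, the target does not meet the requirement stated in the sentence before it. The lung and breast targets were rounded up, from 87 to 90; only the oesophageal target was rounded to a value below its requirement.

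Second, the allowance is multiplied where it should be divided. If 10% of those enrolled contribute nothing to the comparison, then n evaluable patients require n/0.9 enrolled, not n × 1.1.

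What is at stake is the stated 65% power for N status, in the one group for which the plan had already lowered both power and significance level. A reader would take 65% as the agreed minimum for that group.

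**Working it through.** **Inputs (section 4.4).** Oesophageal group, Objective 1.3: two-tailed sign test, alpha 0.10, power 65%, difference 16%, 42 subjects before and 46 after the allowance, target 45, about 10% negative scans. One reading is assumed: the 16% difference is a probability of 0.50 + 0.16 = 0.66 that a differing pair favours one scanner, against 0.50 under the null.

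**Reproducing the base figures.** For n pairs, the exact two-sided sign test rejects when the larger count reaches a critical value u, the smallest integer with P(X ≥ u | n, 0.5) ≤ alpha/2. Power is P(X ≥ u | n, p) + P(X ≤ n − u | n, p). The smallest n that reaches the stated power is:

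| Group, objective | alpha | power | p | exact n | plan |
|---|---|---|---|---|---|
| Lung/breast, 1.1 | 0.05 | 80% | 0.70 | 49 | 49 |
| Lung/breast, 1.3 | 0.05 | 80% | 0.66 | 79 | 79 |
| Oesophageal, 1.1 | 0.10 | 65% | 0.70 | 28 | 28 |
| Oesophageal, 1.3 | 0.10 | 65% | 0.66 | 42 | 42 |

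All four agree, so the exact test and the 0.66 reading are a fair yardstick.

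**The allowance.**

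| Base n | n × 1.1 | plan | n/0.9 | rounded up | target |
|---|---|---|---|---|---|
| 49 | 53.9 | 54 | 54.4 | 55 | 90 |
| 79 | 86.9 | 87 | 87.8 | 88 | 90 |
| 28 | 30.8 | 31 | 31.1 | 32 | 45 |
| 42 | 46.2 | 46 | 46.7 | 47 | 45 |

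Only the last row fails, and it fails by either method.

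**Power with 45 enrolled.** Expected evaluable: 45 × 0.9 = 40.5. Exact power at p = 0.66, alpha 0.10:

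| Evaluable | critical count | power |
|---|---|---|
| 40 | 26 | 62.4% |
| 41 | 27 | 58.0% |
| 42 | 27 | 66.0% |
| 43 | 28 | 61.7% |
| 44 | 28 | 69.2% |
| 45 | 29 | 65.2% |

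The power is saw-toothed because the critical count moves in whole steps. A single n is therefore a poor summary, and it is better to average over a Binomial(N, 0.9) number evaluable:

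| Enrolled N | averaged power |
|---|---|
| 45 | 60.7% |
| 46 | 62.0% |
| 47 | 63.1% |

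**How much is due to the missing patients.** From the 66.0% at exactly 42 evaluable, the fall to 60.7% is about 5 points. Enrolling 46 would recover about 1 point and enrolling 47 about 2. In either case more than half of the fall remains. It comes from the discreteness of the test and from chance variation in the evaluable number.

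**The case against.** The strongest reply is that the plan does not claim this precision. Section 4.4 calls the calculation a rough estimate, puts the negative rate at around 10%, words the target as an aim, and says why oesophageal numbers are limited. A gap of one or two patients is within the uncertainty of the 10% itself. Normal approximations at 40 and 41 evaluable give 64.8% and 65.7% (Noether) or 65.5% and 66.5% (score), so the deficit appears only with the exact test. This stands as a limit on the size of the point. It does not remove it: those approximations give 41 and 40 as the required number, not the plan's 42, and the target still contradicts the requirement printed just before it.

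Three stronger readings are tempting and are not supported.

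- A reader might infer that the missing patients are why 65% is not reached, and that enrolling 46 or 47 would restore it. The averaged figures of 62% and 63% show otherwise.
- A reader might infer that the whole oesophageal sample is too small for its stated power. Objective 1.1 needs 31 by the plan, or 32 by division, and 45 covers both.
- A reader might lower the power further because section 7.1.1 says "A p value of less than 0.05 will be considered to indicate statistical significance". That sentence directly follows the McNemar test. Whether it also governs the oesophageal sign test is a separate question about the significance level and is not part of this mismatch.

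**Conclusion.** The point holds in a limited form. For Objective 1.3 in oesophageal cancer, 45 is below the stated 46 and below the 47 given by division. The power to be expected from 45 patients is about 61% at alpha 0.10, not 65%. It is a minor inconsistency of about 4 percentage points. Every other target in section 4.4 survives the corrected allowance.

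The figures rest on three assumptions: the 16% difference means a 66:34 split, 10% of patients are not evaluable, and every evaluable patient has a different N status on the two scanners. The last is implicit in the plan and favourable to it, because the sign test discards ties and section 4.4 makes no allowance for them. The 61% is therefore the power on the plan's own terms, not a forecast.

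**What to change.** In section 4.4, apply the allowance as n/0.9, giving 55 and 88 for lung and breast and 32 and 47 for oesophageal cancer. Keep the oesophageal target at 45. State that it is below the 47 required for Objective 1.3, and that the power for that objective is about 61% at alpha 0.10 by the exact sign test, averaged over the number evaluable. The total of 225 and the end-of-study definition in section 9.5 do not change, so the cost is a text correction.

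Moving two places to the oesophageal group from lung and breast (89, 89 and 47) is not advised. It would reach only 63.1% there, would take lung and breast from 80.4% to 79.9% on the same averaged measure at alpha 0.05, and would call for more of the patients whom the plan describes as scarce. The significance level for the oesophageal sign test (0.10 in section 4.4, against the 0.05 in section 7.1.1) should be settled as a separate point.
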